## Protocol Body

### **1.0 Background**

Since the introduction of the first laryngeal mask airway, the Classic LMA®, the use of supraglottic airway devices (SGADs) have experienced a remarkable evolution and are now routinely used in clinical anesthesia practice. One of the SGADs on the market is the LMA Protector™ (Teleflex Medical Europe Ltd., [name]), which is a single-use modification of the older, reusable LMA Proseal™ (Teleflex). The LMA Protector™ has a pre-curved, rigid airway tube similar to the Ambu AuraGain™ (Ambu A/S-Copenhagen, Denmark). The concept of a curved airway tube is to imitate the airway anatomy during device placement, thus making insertion relatively easy and smooth. Like some of the newer SGADs, they have a built-in gastric drainage channel to facilitate efflux of gastric fluid and gas, and allows for the insertion of a gastric tube. These devices are referred to as second generation SGADs.

Due to the similarities between the AuraGain™ and the LMA Protector™, a randomized, prospective clinical study with a detailed evaluation of the performance of these two devices will be conducted. The AuraGain™ is Ambu's 3rd generation laryngeal mask, satisfying 3 fundamental airway management needs by integrating gastric access and intubation capability in an anatomically curved single-use device that facilitates rapid establishment of a safe airway. The LMA® Protector™ is a next-generation, single-use laryngeal mask with a dual gastric drainage channel and pharyngeal chamber designed specifically to channel high volume, high pressure gastric contents away from the airway. A clinical evaluation will be performed on elective patients with normal airway anatomy for device insertion, function as a ventilatory device and as an intubation conduit, functionality of the gastric drainage channel, oropharyngeal leak pressure (OLP). Also, a fiberoptic assessment, utilizing the Ambu® aScope™ 3 Slim, of the glottic view via the SGAD device and signs of airway morbidity will be investigated.

### **2.0 Objectives and Hypothesis**

The purpose of this study is to estimate the ratio or difference in success rate of both the Ambu® AuraGain™ and Teleflex® LMA Protector™ during insertion and placement into an airway. Other findings include ease of supraglottic airway device (SGAD) insertion, anatomical fit of the SGAD (i.e. SGAD displacement, bloodstaining), rate of successful ventilation and intubation, functionality of gastric drainage channel (via orogastric tube insertion through each SGAD; to ensure easy insertion), oropharyngeal leak pressure (OLP; measured by a portable, handheld manometer), and postoperative complications in elective surgical patients who are not expected to have a difficult airway. Also, a fiberoptic assessment (with the Ambu® aScope™ 3 Slim) of the glottic view via the SGAD device and signs of airway morbidity will be investigated.

**2.1 Primary:** The ratio or difference in success rates of either the Ambu® AuraGain™ or Teleflex® LMA Protector™ during insertion and placement into an airway.

**2.2 Secondary:** Rate of successful ventilation and intubation (by utilizing the SGAD as an intubation conduit guided by the Ambu® aScope™ 3 Slim), ease of SGAD insertion (based on a numerical subjective rating scale), anatomical fit of SGAD (i.e. SGAD displacement, bloodstaining), OLP (measured by a portable, handheld manometer), functionality of gastric drainage channel which will be inserted through the appropriate channel of the SGAD, and postoperative complications

**2.3 Exploratory:** Fiberoptic assessment of the glottic view via the SGAD device and signs of airway morbidity

### **3.0 Device Description**

The AuraGain™ is Ambu's 2nd generation laryngeal mask, which satisfies three fundamental airway management needs by integrating gastric access and intubation capability in an anatomically curved single-use device that facilitates rapid establishment of a safe airway. AuraGain™ is the only anatomically curved SGAD with integrated gastric access and intubation capability. The integrated gastric access channel is designed with a low friction inner surface to facilitate easy placement of a gastric tube. The AuraGain also provides intubation capabilities in case of an unexpected difficult airway, or a 'Cannot Intubate, Cannot mask Ventilate' (CICV) situation. The AuraGain™ can be used as a conduit for direct endotracheal intubation assisted by a flexible scope (such as the Ambu® aScope3).

The LMA® Protector™ is a next-generation, single-use laryngeal mask with a dual gastric drainage channel and pharyngeal chamber designed specifically to channel high volume, high pressure gastric contents away from the airway. The LMA® Protector™, with its 100% silicone cuff and airway tube, is designed to be gentle to one's airway anatomy. The elongated cuff integrates two technological advancements for facilitating esophageal seal and indicating cuff pressure levels. This enables clinicians to monitor pressure levels at a glance and adjust when necessary. The LMA® Protector™ also allows for intubation with compatible sizes of endotracheal tubes to provide a safer and more effective option for airway replacement.

The Ambu® aScope™ 3 Slim is an ultra slim, single-use, flexible scope that once and for all solves the problem of accessibility, simplifies set-up procedures and eliminates the need for complex cleaning procedures thus releasing valuable resources for other procedures as an alternative to reusable scopes. The Ambu® aScope™ 3 Slim's distal end contains a camera with two LED light sources, a maneuverable tip with a bending angle of 130°/130°, as well as, suction and channel ports (including an ETT connection). When connected to the aView monitor, the Ambu® aScope™ 3 Slim provides high quality images of anatomical landmarks that are suitable for various airway procedures such as intubation, airway inspection, double lumen tube placement, bronchial blocker placement, and even Aintree catheter placement.

### **4.0 Patient Population**

A total of 50 patients will be included in this study to be carried out at the Outpatient Surgical Center by the Department of Anesthesiology and Perioperative Medicine at MD Anderson Cancer Center in the Texas Medical Center, Houston. All patients will be adult surgical candidates, ASA I-III, Age >18 years, Mallampati I – III, BMI ≤ 30 kg/m^2. Patients will be excluded if they meet any of the listed following: ASA IV-V, Age < 18 years old (as the SGADs will not be supplied in pediatric sizes), require prone position for surgery, planned operating time > 4 hours, liquid only diet < 2 hours, are at high risk of regurgitation, exhibit signs of respiratory tract pathology, or have a sore throat preoperatively. In addition, patients with any of the following features

will also be excluded: Mallampati IV, upper lip bite not possible, inter-incisor distance < 2.5 cm, thyromental distance < 6 cm, limited neck movement, airway pathology/facial abnormality, diagnosed with dementia or exhibit any neurological mental disorders (handicaps) such as epilepsy, Alzheimer's disease, Parkinson's disease, etc.

### **Inclusion Criteria**

Subjects enrolled in this study will meet the following inclusion criteria:

- 1) Age 18 years of age or older
- 2) Scheduled for an elective surgery requiring general anesthesia
- 3) Scheduled surgery < 4hrs
- 4) American Society of Anesthesiology (ASA) Physical Status I-III
- 5) BMI  $\leq$  30 kg/m^2
- 6) Mallampati I-III
- 7) Able to bite upper lip via Upper Lip Bite Test (ULBT)
- 8) Inter-incisor distance > 2.5cm
- 9) Thyromental distance > 6cm
- 10) Full range of motion in the neck
- 11) Has provided written informed consent

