## **6.0 Subject Identification, Recruitment and Consent**

### **Discussion of Subject Population**

Patients that elect to have surgery typically require general anesthesia and tracheal intubation. Tracheal intubation is usually achieved, traditionally, by direct or indirect laryngoscopy, and is the preferred method when securing an airway. SGADs are the recommended alternative to laryngoscopy via laryngoscopes if failed or not possible, to aid in sufficient oxygenation and ventilation of patients according to difficult airway algorithms. Therefore, SGADs are constantly studied for significance and adequacy as a rescue device for emergent scenarios or when laryngoscopy fails.

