## 8.0 Study Intervention and Data Collection

This study involves the placement and usage of a laryngeal mask airway on a human subject for adequate airway management, oxygenation, and ventilation. The intervention directly related to this study is that of airway management, airway device/equipment, oxygen administration, mechanical ventilation, fiberoptic assistance, and tracheal intubation. The subject will have a surgical procedure that is incidental to his or her study participation, along with tracheal intubation. Besides the principal investigator and co-investigator, listed collaborators (anesthesiologists) will be involved in managing enrolled patient airways in accordance to the protocol. Randomization of the anesthesia practitioner is not necessary and will not occur. All patients will be recruited and enrolled based on the availability of the 8 study anesthesiologists during the study period.

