## 5. Use of SGAD as an Intubation Conduit

### 1) Intubation Procedure

An intubation procedure will be performed by placement of an ETT over the Ambu aScope3 Slim. A standard use Parker Flex Tip™ ETT of maximum recommended size will be used depending on SGAD size for both female and male patients. ETTs of 6.0, 7.0, and 8.0 mm will be paired with the AuraGain, sizes 3, 4, and 5 respectively. An ETT of 6.0 mm will be paired with the LMA Protector size 3, and ETTs of 7.0 and 8.0 mm will be paired with the LMA Protector, sizes 4 and 5 respectively. The airway tube of the SGAD will be lubricated and the aScope3 Slim will be passed through the airway tube until carina is visualized. Once the aScope3 Slim is at the carina, the ETT will be passed down the insertion cord of the aScope3 Slim and correct placement of the ETT will be verified. Once the ETT is placed correctly, the cuff of the ETT will be inflated and the aScope3 Slim will be removed.

An intubation attempt will be defined as from when the tip of the ETT is touching the SGAD connector and advanced through the SGAD. If an unsuccessful attempt occurs, and the ETT is withdrawn from the SGAD, the next attempt will be considered a new attempt. No more than 3 intubation attempts shall be made for proper ETT placement. If unsuccessful after 3 attempts with at least 2 different size SGAD devices used, standard tracheal intubation will be performed.

Intubation time will be measured from when the tip of the aScope3 Slim is touching the SGAD connector until endoscopic confirmation of correct ETT placement. End-tidal capnography will be used to confirm successful intubation. In addition, size of SGAD, size of ETT, and number of intubation attempts will also be recorded. Qualitative assessment of ease of intubation, and will be based on an analog scale from 1-4: 1: Easy 2: Resistance 3: Difficult 4: Unsuccessful.

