## 9.0 Risks and Benefits

### Risks

In general, subjects will be a part of a study that may potentially affect how anesthetic providers practice and manage difficult airway patients. As a specific benefit, subjects will be intubated using a new video laryngeal mask airway. Risks are similar to a regular laryngeal mask airway, including but not limited to, device malfunction and airway adverse events.

As with use of all medical devices, complications may occur. Recognized risks associated with the use of the study intervention include, but are not limited to, the following:

- Allergic reactions: although the materials being used are hypoallergenic and the risk is small, there remains a risk for an allergic reaction that may result in hives, swelling, or anaphylaxis.
- Oropharyngeal injury: although the both LMA were designed for supraglottic placement, some bleeding/bloodstaining may occur upon placement
- Oropharyngeal pressure: over inflation of the both LMA can occur that can cause an increase in pressure

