#### Alternatives to Participation

The alternative for not participating in this study would result in not using either SGAD for tracheal intubation. Therefore, a traditional alternative (the standard of care) such as a laryngoscope would be utilized for tracheal intubation.

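### Eligibility requires only general anesthesia, yet intubation is performed without a condition of clinical need and the alternatives statement assumes that a non-participant would be intubated anyway

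*Combined protocol and SAP*

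**What the plan says.** Eligibility (Section 4.0, Inclusion Criteria, item 2): the patient must be "Scheduled for an elective surgery requiring general anesthesia". The other ten inclusion criteria, the 14 exclusion criteria and the narrative that opens Section 4.0 do not mention intubation.

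Procedure (Section 8.0, Use of SGAD as an Intubation Conduit): "An intubation procedure will be performed by placement of an ETT over the Ambu aScope3 Slim". Up to three attempts are allowed. If they fail, with at least two SGAD sizes tried, "standard tracheal intubation will be performed". Neither step depends on a clinical need for intubation.

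Status of intubation (Section 8.0, opening paragraph): the components of the intervention directly related to the study end with "fiberoptic assistance, and tracheal intubation". The next sentence reads: "The subject will have a surgical procedure that is incidental to his or her study participation, along with tracheal intubation".

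Usual care (Section 6.0, Discussion of Subject Population): "Patients that elect to have surgery typically require general anesthesia and tracheal intubation".

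Alternatives (Section 9.0, Alternatives to Participation): for a patient who does not take part, "a traditional alternative (the standard of care) such as a laryngoscope would be utilized for tracheal intubation". No alternative without intubation is named.

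Risks (Section 9.0, Risks): "Risks are similar to a regular laryngeal mask airway, including but not limited to, device malfunction and airway adverse events". The itemized risks are allergic reaction, oropharyngeal injury and cuff over-inflation.

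**The concern.** The alternatives statement is accurate only for patients who would be intubated in any case, and the eligibility criteria do not confine enrolment to them. The protocol's own background says that SGADs are in routine anesthetic use, and the trial takes elective cases planned for under 4 hours at an outpatient surgical center. A patient whose planned anesthetic uses an SGAD alone could meet all 11 inclusion criteria and no exclusion criterion.

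For such a patient, passing a tracheal tube, with up to three attempts through the SGAD and a standard intubation after failure, would be done for the study. The protocol would describe that patient's alternative wrongly and would measure the risk against an ordinary laryngeal mask. What is at stake is exposure to a procedure that the patient did not otherwise need, and the accuracy of the protocol's account of risks and alternatives.

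**Working it through.** No calculation in the plan bears on this point, so the check is a comparison of texts, followed by its possible size.

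**1. Does any eligibility rule require planned intubation?** No. Inclusion item 2 stops at general anesthesia. Several other criteria concern airway anatomy (Mallampati class, upper lip bite, inter-incisor and thyromental distance, neck movement), but none concerns the airway plan.

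**2. Does the procedure depend on clinical need?** No. Section 8.0 states the intubation step without such a condition, and the fallback is also intubation.

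**3. Does the protocol establish that every eligible patient would be intubated anyway?**

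| Place | What it implies about intubation |
|---|---|
| Section 6.0, Discussion of Subject Population | Usual, but qualified by *typically* |
| Section 8.0, opening paragraph, list of interventions | Part of the study intervention |
| Section 8.0, opening paragraph, next sentence | Accompanies the incidental surgery |
| Section 9.0, Alternatives to Participation | Standard of care for anyone who declines, without qualification |

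Section 6.0 allows exceptions, Section 9.0 allows none, and the opening of Section 8.0 points both ways. The unqualified statement in Section 9.0 therefore goes further than its support.

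**4. Does another provision close the gap?** Consent Process (Section 6.0) requires permission from the faculty anesthesiologist in charge of the patient's anesthesia care. Section 7.0 allows withdrawal by clinician decision. Neither is tied to a need for intubation. Rocuronium in Section 8.0 is given ahead of SGAD insertion as part of the study sequence, so it does not show what the patient would have had outside the study. The baseline items listed in Section 5.0 do not include the planned airway.

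**5. Possible size.** If q is the share of enrolled patients whose usual care would not include intubation, the expected number is 50 × q. The documents give no value of q. As assumptions only:

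- q = 0%: 50 × 0 = 0
- q = 10%: 50 × 0.10 = 5
- q = 20%: 50 × 0.20 = 10
- q = 40%: 50 × 0.40 = 20

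Zero is a legitimate value: it is what Section 9.0 implies if taken at its word.

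**6. Effect on the planned statistics.** Section 11.0 defines success as SGAD placement on the first attempt. In Section 8.0 that is step 1 and intubation is step 5, so the primary endpoint is settled before any intubation. The design interval also reproduces, with rates 0.90 and 0.98 and 25 per arm:

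- RR = 0.98 / 0.90 = 1.089
- SE of log RR = √[0.10/(25 × 0.90) + 0.02/(25 × 0.98)] = √(0.004444 + 0.000816) = 0.0725
- 95% limits = 1.089 × exp(±1.96 × 0.0725) = 0.945 and 1.255

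These match the stated limits, and nothing in this point changes them.

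**The case against.** The strongest reply is that the affected group is inferred. Nothing in the documents shows that a candidate at this center would have an SGAD-only anesthetic. Routine SGAD use is a general background remark, Section 6.0 calls intubation the preferred way to secure an airway, and an outpatient setting proves nothing by itself. This stands. A reader might infer that some participants will be intubated purely for research, but the documents support only that they could be.

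A reader might also infer that consent would be invalid. The documents do not support that. The consent form is not among the material available, and Section 6.0 requires the explanation to separate research from standard of care and to cover risks, benefits and alternatives. The point is therefore limited to the protocol text.

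It is also fair to say that Section 8.0 does list tracheal intubation as study intervention, and that the Risks text tells the reader that subjects will be intubated and leaves its list of risks open-ended. So the protocol does not conceal the procedure. What remains is that the adjoining sentence in Section 8.0 points the other way, no intubation-specific risk is itemized, and the alternatives statement is unqualified.

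Finally, a reader might infer that mixing patients with and without clinically planned intubation distorts the comparison of postoperative complications. It does not. Allocation is randomized 1:1, and the same intubation procedure applies in both arms whatever the clinical plan was.

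**Conclusion.** The inconsistency is real and lies in the protocol text. Followed as written, the plan can enrol a patient whose usual care would not include intubation. For that patient the intubation is a research procedure, the alternatives statement is untrue, and no risk specific to intubation is listed. Permission from the anesthesiologist and withdrawal by the clinician are partial safeguards, because neither turns on a need for intubation.

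The number of such patients is unknown and may be zero. The counts shown above rest on assumed shares and carry no weight in the conclusion, which needs only that such enrolment is possible. The point is worth correcting because it bears on patient safety and on the description of risks and alternatives, and because the correction is small. It does not touch the primary endpoint, the sample-size interval or the comparison between arms.

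**What to change.** Before enrolment, reconcile inclusion item 2 (Section 4.0), Discussion of Subject Population (Section 6.0), the opening paragraph and the intubation procedure in Section 8.0, and Risks and Alternatives to Participation (Section 9.0). There are two consistent outcomes:

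- If the population implied by the incidental-surgery sentence in Section 8.0 and by Section 9.0 is intended, extend inclusion item 2 to say that tracheal intubation is already part of planned care, confirmed before consent.
- If the wider population is intended, state that the study adds intubation for some participants, list its risks, give the true alternatives, and record on the case report form whether intubation was clinically planned.

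In either case the opening paragraph of Section 8.0 should describe intubation in one way, and the consent form should be checked against the revised text. Which population is intended is for the sponsor and investigator to decide.

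The cost is a protocol amendment of one criterion or a short passage on risks and alternatives, with a consent amendment if the form needs one. Recruitment may be slower if eligibility is narrowed. The second outcome adds one data item. Neither adds a procedure or staff.

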### **Exclusion Criteria**

Subjects will not be enrolled in this study if they meet any of the following exclusion criteria:

- 1) Under the age of 18 years old
- 2) ASA IV-V
- 3) Require prone positioning for surgery
- 4) Scheduled surgery > 4hrs
- 5) Liquid only diet < 2hrs and/or solids < 8hrs
- 6) High risk of regurgitation
- 7) Exhibits signs of respiratory tract pathology (including a sore throat preoperatively)
- 8) Mallampati IV
- 9) Unable to bite upper lip via ULBT
- 10) Inter-incisor distance < 2.5cm
- 11) Thyromental distance < 6cm
- 12) Limited neck movement
- 13) Airway pathology/facial abnormality
- 14) Has been diagnosed with/exhibits any mental neurological disorder/disease/condition that would prevent participation in the study in the opinion of the investigator.

## **5.0 Randomization**

CORe will be the designated software for the randomization of each intervening device (SGAD) arm. The treatment will be named 1 for Ambu® AuraGain™, 2 for Teleflex® LMA Protector™ for both parts of the study in the list. Block randomization is 25 blocks of size of 2.

The following demographic data and medical history will be collected on the case report form (CRF): Gender, age, height, weight, body mass index, fasting time, ASA class, Mallampati classification, thyromental distance, sternal distance, interincisor distance, and ability to protrude lower jaw. Please refer to Appendix 'C'.

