### **Method Of Subject Identification And Recruitment**

Eligible subjects will receive a detailed explanation of the study, its purpose, their role, and study procedures in relation to what's considered research and standard of care (SOC); as well as the potential risks, benefits and alternatives prior to study enrollment. They will be given a consent form to read and if they so choose, to discuss with friends, family, and other clinicians. They will be invited to ask questions and, after all questions are answered to their satisfaction, invited to sign the consent form in accordance. The Principal Investigator (or delegate) will participate in the consenting process to ensure the subject has full understanding of the procedure and risks. No study-specific procedure will be performed before the consent form is signed.

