### **Consent Process**

Eligible subjects will receive a detailed explanation of the study, its purpose, their role, and study procedures in relation to what's considered research and standard of care (SOC); as well as the potential risks, benefits and alternatives prior to study enrollment. They will be given a consent form to read and if they so choose, to discuss with friends, family, and other clinicians. They will be invited to ask questions and, after all questions are answered to their satisfaction, invited to sign the consent form in accordance. The Principal Investigator (or delegate) will participate in the consenting process to ensure the subject has full understanding of the procedure and risks. No study-specific procedure will be performed before the consent form is signed.

Subject participation in this investigation is voluntary. Written informed consent is required from all subjects prior to the subject's participation in the investigation. Also, an obtained permission of the faculty anesthesiologist, in charge of the patient's anesthesia care, must also be granted for subject participation. If the subject is illiterate or unable to adequately read the informed consent form, a witness' signature and a cross mark or a fingerprint of the subject is required. In accordance with FDA regulation 21 CFR Part 50, informed consent shall be obtained prior to any study procedure. The original of the signed consent

will be retained at the investigational site. A signed copy of the consent will be given to the subject. While not anticipated, Sponsor will report any failure to obtain subject consent to the IRB within 5 days of learning of such an event, as required by regulation.

Prior to participating in this investigation, the site will be required to have an IRB-approved Informed Consent Document. Any modifications to the consent must be approved by Sponsor and by the IRB of record. The Principal Investigator at each study site is responsible for obtaining and maintaining the approved informed consent and forwarding an IRB-stamped copy to Sponsor.

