### Patient Preparation Procedures

Prior to the surgical procedure, patient demographics and airway assessment will be recorded, as well as the selected randomized SGAD that will be used to secure the airway. The patient will be monitored with 5-lead ECG, pulse oximetry, non-invasive blood pressure (BP) and end-expiratory gas analysis. Vital sign measurements will be taken and recorded at the following time points: Pre-oxygenation, pre-induction, post-induction, post-SGAD insertion, 10 minutes after SGAD insertion, on admission to the post anesthesia recovery unit (PACU), and every 30 minutes until discharge from PACU. The patient will be positioned supine on the operating table with the head resting on a foam cushion and/or pillows and blankets (if needed). The patient will be pre-oxygenated via full facemask for a minimum of 3 minutes. Prior to pre-oxygenation, the circle system will be filled with 100% oxygen. The flow of oxygen will be set at 10 liters to obtain the highest end tidal concentration of oxygen (EtO2).

General anesthesia will be induced via traditional methods as requested by the anesthesiologist. Appropriate doses of propofol, fentanyl, and rocuronium will be administered as recommended by the anesthesiologist's discretion. A mixture of sevoflurane or desflurane will be utilized for maintenance of anesthesia. Vital signs will be recorded throughout. Lungs will be mechanically ventilated with a semi-closed circle system to maintain an end-tidal CO2 near 35mmHg. Once there are no twitches on the train of four (ToF) twitch monitor, following rocuronium administration, insertion of the randomized SGAD will then be performed. The size of the SGAD device used will be based on the manufacturers' recommendations or by clinical evaluation of the patient the anesthesiologist.

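### Fixed, disclosed blocks of 2 make 25 of the 50 device assignments certain to anyone who knows the running allocations

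*Combined protocol and SAP*

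**What the plan says.** Section 5.0 names CORe as the randomization software, codes the two devices 1 and 2, and fixes the scheme: "Block randomization is 25 blocks of size of 2". It names no stratification factor, no list holder and no point at which an assignment is released. It applies the coding "for both parts of the study in the list", but nothing explains what the parts are.

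Section 6.0 says "The Principal Investigator (or delegate) will participate in the consenting process" and "No study-specific procedure will be performed before the consent form is signed". Its Consent Process text adds a second condition: "an obtained permission of the faculty anesthesiologist, in charge of the patient's anesthesia care, must also be granted for subject participation".

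Section 8.0 describes who handles the airway and how patients enter: "Besides the principal investigator and co-investigator, listed collaborators (anesthesiologists) will be involved in managing enrolled patient airways", and "All patients will be recruited and enrolled based on the availability of the 8 study anesthesiologists during the study period". Under Patient Preparation Procedures, before surgery, "patient demographics and airway assessment will be recorded, as well as the selected randomized SGAD that will be used to secure the airway". The same section says that practitioners are not randomized.

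Under Subject Data Confidentiality, Section 12.0 places the data logbook in the principal investigator's locked office and gives registered investigators access to a password-protected file.

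Section 11.0 defines success as insertion and placement on the first attempt, and assumes 25 patients per arm.

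**The concern.** Two is the smallest possible 1:1 block and the most predictable, and the protocol that staff work from prints the size. Hiding the list does not help, because the second slot follows from the first.

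The principal investigator is plausibly placed to make that deduction. The role takes part in consent, directly or through a delegate, is among those managing study airways, and keeps the logbook. The faculty anesthesiologist's permission and the dependence on staff availability are points where knowledge of the next device could affect who is put forward, or when. The consent rules do not say when the assignment is released, and they do not prevent the deduction.

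First-attempt success may depend partly on the patient. If easier patients tend to reach one device, the primary ratio or difference shifts. Section 10.0 plans unadjusted between-arm tests, and selection bias cannot be reliably repaired at analysis.

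**Working it through.** **Inputs.** 50 patients (Section 4.0); 25 blocks of 2 (Section 5.0); 8 anesthesiologists (Section 8.0); 25 per arm with success rates 0.90 and 0.98 (Section 11.0). One unstratified list, filled in order, is assumed.

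**The plan's own figures.** 25 × 2 = 50, with one patient per arm in each block, so 25 per arm. For the relative risk, 0.98/0.90 = 1.089, with log-scale standard error √[0.10/(25 × 0.90) + 0.02/(25 × 0.98)] = 0.0725. The 95% interval is 0.945 to 1.255, as Section 11.0 states. Block size does not affect it.

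**Predictability of the current list (exact).** In each block the first slot is a 50% guess and the second is certain.
- Certain: 25 × 1 = 25 of 50 (50%).
- Best-guess accuracy: (0.5 + 1)/2 = 75%, or 37.5 of 50.

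If the two parts meant separate lists, the second slot of every complete block would still be certain.

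**A clinician who sees only their own cases.** Assume 8 equally busy anesthesiologists, each taking runs of L consecutive patients placed at random against the blocks, with the next clinician drawn at random from the 8. A second slot is certain if the same clinician had the first. Summed over all 8, the number certain is 25 × [(L−1)/L + 1/(8L)].

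| Run length L | Certain, block start known | Certain, block start unknown (simulated) |
|---|---|---|
| 1 | 3.1 | 0.2 |
| 2 | 14.1 | 1.6 |
| 3 | 17.7 | 5.5 |

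In the last column the clinician knows which of their cases are consecutive, but is certain only after seeing the same device twice running.

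**Alternative list.** Five blocks of 4 and five of 6 in random order: 5 × 4 + 5 × 6 = 50. Simulated against an optimal guesser who knows this composition and every earlier allocation:
- about 4.4 of 50 certain (8.8%; 5th to 95th percentile 1 to 9);
- about 69% accuracy;
- maximum running imbalance 3.

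If sizes 4 and 6 are instead drawn at random for each block, about 2.8 are certain. Fixed blocks of 4 would leave 16.7 certain, and fixed blocks of 6 would leave 12.5.

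**Illustration of possible bias.** Assume identical devices and two equally common patient types with success rates 0.98 and 0.90. These rates are assumed for patients; the documents do not give them. Staff steer the better type to one device.
- Current list: bias = gap × 0.50 × fraction of predictable slots steered. All steered: 0.08 × 0.50 = 0.040, or 4.0 points. A quarter steered: 0.040 × 0.25 = 0.010, or 1.0 point.
- For gaps of 2 to 10 points: 1.0 to 5.0 points if all are steered, and 0.25 to 1.25 if a quarter are.
- Alternative list, acting on every best guess: 0.08 × (2 × 0.694 − 1) = 0.031, or 3.1 points. Acting only on certainty: 0.08 × 0.088 = 0.007, or 0.7 points.

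For scale, the half-width of the 95% interval for the difference is 1.96 × √(0.90 × 0.10/25 + 0.98 × 0.02/25) = 0.130, or 13 points.

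**The case against.** The strongest objection is about access. The figure of 25 needs someone who follows every allocation, and the documents do not show that allocations are listed in order or consulted at enrolment. The logbook is locked, the file is password-protected, and CORe's settings are not given. For staff other than the principal investigator, this points away from easy tracking. That stands as a limit: access is inferred. It does not remove the exposure, because nothing in the plan prevents tracking.

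The own-case counts depend on invented caseload patterns and on knowing where blocks start. Without that knowledge they fall to between 0.2 and 5.5. This is right, and it bounds a secondary scenario only.

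The 4.0 points are a ceiling. They need perfect recognition of patient type, free choice for every predictable slot, and everyone favouring the same device; opposing preferences would partly cancel. Section 4.0 already excludes predicted difficult airways, and scheduled elective surgery with enrolment tied to staff availability limits freedom over timing. All of this stands. Yet Mallampati I–III, ASA I–III and BMI up to 30 remain eligible, so patients can still differ.

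Varied blocks also gain little against a best guesser: accuracy falls only from 75% to about 69%. The main gain is the removal of certainty. Choices of operator and device size made after the device is known stay open, and they need no prediction.

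**Conclusion.** The concern holds and should be fixed before enrolment. For a person who knows the running allocations, 25 of 50 assignments are certain and best-guess accuracy is 75%. Both figures are exact for one list filled in order. That someone has this knowledge is a plausible inference from the overlapping roles, not something the documents state. The effect on the primary result cannot be computed from the documents; the illustrated biases of 1.0 and 4.0 points rest on assumed patient success rates and assumed steering. The sample size and the precision stated in Section 11.0 are unaffected.

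**What to change.** In Section 5.0, replace the sentence on block size with:

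> Allocation is 1:1 in permuted blocks of varying size, 25 per arm. Block sizes are held in a separate document not available to staff who enrol patients or insert devices. CORe releases each assignment only after consent and anesthesiologist permission are recorded.

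The separate document could specify, for example, five blocks of 4 and five of 6 in random order. Section 5.0 should also explain or delete its reference to two parts of the study.

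The cost is three sentences, a regenerated list and a temporary imbalance of up to 3 patients; the final split stays 25:25. This assumes that CORe can use varying blocks and hold back an assignment until both conditions are recorded, which the documents do not show and the sponsor should confirm. Section 10.0's general between-arm methods can be applied to the baseline airway data listed in Section 5.0 without a new analysis, although Section 10.0 does not name that comparison. The change does not address choices of operator or device size made after the assignment is known.
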